#### **General Physical Examination Findings**

At screening, any clinically significant abnormality should be recorded as a preexisting condition. At the end of the study, any new clinically significant findings/abnormalities that meet the definition of an adverse event must also be recorded and documented as an adverse event.

#### **Post-study Adverse Event**

All unresolved adverse events should be followed by the investigator until the events are resolved, the subject is lost to follow-up, or the adverse event is otherwise explained. At the last scheduled visit, the investigator should instruct each subject to report any subsequent event(s) that the subject, or the subject's personal physician, believes might reasonably be related to participation in this study. The investigator should notify the study sponsor of any death or adverse event occurring at any time after a subject has discontinued or terminated study participation that may reasonably be related to this study. The sponsor should also be notified if the investigator should become aware of the development of cancer or of a congenital anomaly in a subsequently conceived offspring of a subject that has participated in this study.

#### **Abnormal Laboratory Values**

A clinical laboratory abnormality should be documented as an adverse event if any one of the following conditions is met:

- The laboratory abnormality is not otherwise refuted by a repeat test to confirm the abnormality
- The abnormality suggests a disease and/or organ toxicity
- The abnormality is of a degree that requires active management; e.g. change of dose, discontinuation of the drug, more frequent follow-up assessments, further diagnostic investigation, etc.

Because baclofen is principally renally excreted individuals with elevated creatinine or reduced GFR will be excluded. Additionally, creatinine and a liver profile will be monitored at 4, 8 and 12 weeks and, if creatinine is elevated or AST/ALT levels  $> 5 \times$  ULN, medication will be stopped. Participants will be given a card to carry with them to inform health care personnel that the individual may be on baclofen.

### **Hospitalization, Prolonged Hospitalization or Surgery**

Any adverse event that results in hospitalization or prolonged hospitalization should be documented and reported as a serious adverse event unless specifically instructed otherwise in this protocol. Any condition responsible for surgery should be documented as an adverse event if the condition meets the criteria for an adverse event.

Neither the condition, hospitalization, prolonged hospitalization, nor surgery are reported as an adverse event in the following circumstances:

- Hospitalization or prolonged hospitalization for diagnostic or elective surgical procedures for a preexisting condition. Surgery should **not** be reported as an outcome of an adverse event if the purpose of the surgery was elective or diagnostic and the outcome was uneventful.
- Hospitalization or prolonged hospitalization required to allow efficacy measurement for the study.
- Hospitalization or prolonged hospitalization for therapy of the target disease of the study, unless it is a worsening or increase in frequency of hospital admissions as judged by the clinical investigator.

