#### 4.2 Exclusion Criteria

1. Clinically significant medical disease that might interfere with the evaluation of the study medication or present a safety concern (e.g., renal insufficiency, cirrhosis, unstable hypertension, diabetes mellitus, seizure disorder). Clinically significant psychiatric illness including any psychotic disorder, bipolar disorder, severe depression, or suicidal ideation.
2. Other substance abuse or dependence disorder other than nicotine or alcohol or cannabis abuse. Occasional use of cocaine is acceptable.
3. Concurrent use of any psychotropic medication including antidepressants, mood stabilizers, antipsychotics, anxiolytics, stimulants, or hypnotics with the exception of stable doses of antidepressants for one month. Concurrent use of anticonvulsants, insulin, or oral hypoglycemics.
4. Prior history of adverse reaction to baclofen.
5. Estimated Glomerular Filtration Rate  $<$  age norm.
6. AST, or ALT  $>$  5 times ULN or bilirubin  $>$  1.5 X ULN.
7. Positive urine toxicology screen with the exception of cannabis. Individuals with positive cannabis screens will be excluded only if they have a history of cannabis dependence.

8. Pregnant women and women of childbearing potential who do not practice a medically acceptable form of birth control (oral or depot contraceptive, or barrier methods such as diaphragm or condom with spermicidal).
9. Women who are breastfeeding.
10. Individuals requiring inpatient treatment or more intense outpatient treatment for their alcohol dependence.
11. Participation in any clinical trial within the past 60 days.
12. Court-mandated participation in alcohol treatment or pending incarceration.

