#### Adverse Event

An **adverse event** (AE) is any symptom, sign, illness or experience that develops or worsens in severity during the course of the study. Intercurrent illnesses or injuries should be regarded as adverse events. Abnormal results of diagnostic procedures are considered to be adverse events if the abnormality:

- results in study withdrawal
- is associated with a serious adverse event
- is associated with clinical signs or symptoms
- leads to additional treatment or to further diagnostic tests
- is considered by the investigator to be of clinical significance

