#### Serious Adverse Event

Adverse events are classified as serious or non-serious. A **serious adverse event** is any AE that is:

- fatal
- life-threatening
- requires or prolongs hospital stay
- results in persistent or significant disability or incapacity
- a congenital anomaly or birth defect
- an important medical event

Important medical events are those that may not be immediately life threatening, but are clearly of major clinical significance. They may jeopardize the subject, and may require intervention to prevent one of the other serious outcomes noted above. For example, drug overdose or abuse, a seizure that did not result in in-patient hospitalization, or intensive treatment of bronchospasm in an emergency department would typically be considered serious.

All adverse events that do not meet any of the criteria for serious should be regarded as ***non-serious adverse events***.

For the purpose of this trial the following events are expected side effects of the drug:

- Drowsiness
- Weakness
- Dizziness/lightheadedness
- Nausea/vomiting
- Headache
- Insomnia
- Lethargy/fatigue
- Frequent urination
- Constipation
- Confusion
- Hypotension
- Blurred vision
- Seizures (rare)

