**8.6 Medical Monitoring**

The study PI, [name], will be responsible for monitoring participant safety during the trial and will be assisted by other study physicians and research coordinators. [name] has extensive experience in clinical trials for alcohol dependence including previous experience with baclofen. Serious adverse events will be reported to the IRB, to the DSMB and to the NIAAA project officer within 24 hours. An annual report documenting all adverse events will be submitted to the NIAAA project officer.

Participants will be contacted by telephone 4 weeks after the final trial visit to ascertain drinking behavior and any physical or psychiatric problems. Individuals with clinically significant problems will be referred for appropriate psychiatric or medical treatment.

No alcohol will be administered to any individual as part of this research project.

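### Admissions to treat alcohol dependence are conditionally exempt from AE and SAE reporting, on an investigator judgement whose terms the protocol does not define

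*Combined protocol and SAP*

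**What the plan says.** The part of section 8.1 on hospitalization and surgery starts from a default: "Any adverse event that results in hospitalization or prolonged hospitalization should be documented and reported as a serious adverse event unless specifically instructed otherwise". It then lists exceptions under the sentence "Neither the condition, hospitalization, prolonged hospitalization, nor surgery are reported as an adverse event in the following circumstances". The third exception is "Hospitalization or prolonged hospitalization for therapy of the target disease of the study", and it is qualified: "unless it is a worsening or increase in frequency of hospital admissions as judged by the clinical investigator". In this trial the disease is alcohol dependence.

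Other rules bear on the same admissions:

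- The AE definition in section 8.1 covers "any symptom, sign, illness or experience that develops or worsens in severity during the course of the study".
- The preexisting-condition paragraph in section 8.1 makes worsening in frequency, intensity or character an AE.
- The SAE definition in section 8.1 lists a required or prolonged hospital stay with no exception for the target disease. Its examples of important medical events include "drug overdose or abuse, a seizure that did not result in in-patient hospitalization".
- Section 8.2 requires every AE in the study period to be recorded.
- Section 4.2, criterion 10, excludes "Individuals requiring inpatient treatment or more intense outpatient treatment for their alcohol dependence".
- Section 8.6: "Serious adverse events will be reported to the IRB, to the DSMB and to the NIAAA project officer within 24 hours".

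**The concern.** Safety of both doses against placebo is part of the primary objective (section 2). The trial gives a drug with CNS depressant properties (sections 1.2 and 5.1) to people who need not be abstinent at randomisation (section 6, Initial Treatment Visit). The list of expected effects in section 8.1 includes drowsiness, confusion and seizure. Seizure is also named as a withdrawal problem in section 4.3. So an alcohol-related admission can resemble a drug effect.

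The exemption makes the cause of an admission decide whether it is an AE at all. The investigator who makes that decision does not know the allocation (section 8.4). The usual order is to capture the event first and assess causality afterwards.

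An event that is classed as exempt need not appear in the AE or SAE tables and does not trigger the 24-hour report. That report matters here because two other routes, the minimum reporting set in section 8.3 and the FDA expedited reports in section 8.3.2, require the event to be unexpected, and the three overlapping effects are listed as expected. The participant-level rule in sections 4.4 and 8.5 for possibly related serious events is also tied to SAE classification.

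**Working it through.** The plan gives no figure to reproduce: no expected admission rate, no safety threshold and no safety sample size. The check is to take the rules together and follow three kinds of admission through them.

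**1. Entrant from Freedom House, admitted again for detoxification.** Section 6 says that these entrants come in after detoxification, and section 4.3 treats them as a sought-after group. A further stay can be read as therapy of the target disease. With a recent stay as the comparison, it need not look like an increase in frequency, and a similar episode need not look like worsening. On that reading neither the condition nor the admission is reported. Under the AE definition, a relapse that develops on study would be an AE. The two rules give different answers.

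**2. Entrant recruited by advertisement, first alcohol admission on study.** Criterion 10 means that this person did not need inpatient care at entry. An admission is then naturally a worsening or an increase, so the exception applies and the SAE default returns. The likely result is that it is reported, although no definition compels it.

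**3. Any participant admitted with seizure, confusion or drowsiness after drinking or during withdrawal.** Under the SAE definition, a seizure that does not lead to admission is typically serious. If the person is admitted and the stay is labelled treatment of alcohol withdrawal, the exemption may be read to apply. The more serious course could then have the weaker reporting duty. The exemption does not mention intoxication or withdrawal, so this depends on how it is read.

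**Does section 8.2 close the gap?** Not clearly. It requires all AEs to be recorded, but the exemption operates one step earlier, on whether the condition and the admission are reported as an AE.

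**Scale.** Section 7.1 plans 120 participants, 40 per arm. For x events among 40, the exact one-sided 95% upper limit is the p that solves

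Σ (i = 0 to x) C(40, i) · p^i · (1 − p)^(40 − i) = 0.05.

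- x = 0: p = 1 − 0.05^(1/40) = 7.2%.
- x = 1: p = 11.3%. Check: 0.887^40 + 40 × 0.113 × 0.887^39 ≈ 0.008 + 0.042 = 0.050.
- x = 2: p = 14.9%. Check: 0.851^40 + 40 × 0.149 × 0.851^39 + 780 × 0.149² × 0.851^38 ≈ 0.002 + 0.011 + 0.038, about 0.05.

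One or two events in an arm, counted or not, therefore move the upper limit from 7.2% to 11.3% or 14.9%. These figures show how sensitive a 40-person arm is. They do not estimate how many events would be lost.

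**The case against.** The strongest reply is that the exemption is narrow and other rules surround it.

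- It is conditional. A reader who stops at the exempted circumstance might infer that all alcohol admissions are excluded. The qualifier rules that out, and criterion 10 means that many on-study admissions would meet it. This stands, and it confines the clearest gap to entrants with a recent detoxification stay. Even there, worsening is a separate trigger from frequency.
- A reader might infer that such events go unrecorded. The documents do not support that. Section 8.2 requires questioning about AEs at each contact, the schedule in section 6 collects AEs at every treatment visit, and new drowsiness, confusion or seizure has its own route through the AE and SAE definitions. The supportable wording is that the admission and its condition may not be reported as an AE or SAE.
- The wording covers therapy of the disease and does not name intoxication or withdrawal. This is correct, and it is part of the difficulty: the documents do not say which side of the line those admissions fall on.
- A reader might infer that the DSMB is the only safeguard, since section 8.5 sets no stopping rules in advance. It is not. The principal investigator monitors safety and the funder receives all AEs annually (section 8.6), the board receives unblinded summaries (section 8.6.1), and the IRB and FDA have their own reports (section 8.3). However, the annual report covers AEs, so it need not include an event classed as exempt.
- Section 1.1 describes baclofen as appearing relatively safe with alcohol, and nothing in the documents shows that admissions would be lost unequally. Both points stand.

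None of these replies supplies the missing definitions or settles which rule governs when two apply to the same admission.

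**Conclusion.** The concern holds in a limited form. The protocol contains an explicit, conditional exemption that covers both the condition and the admission. Its operation rests on three undefined terms and a blinded judgement made before capture, and it is not reconciled with the AE, SAE, preexisting-condition and recording rules. An alcohol-related admission judged neither worse nor more frequent can be absent from the AE and SAE data and from the 24-hour report.

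The size is unknown. The documents give no admission rate and no way to tell how often the investigator would apply the exception. Statements that most serious events would be lost, or that loss would be greater on 90 mg/d, have no support in the documents; differential loss is possible, not shown. The limits of 7.2%, 11.3% and 14.9% assume 40 evaluable participants per arm and are for scale only.

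This is a worthwhile, low-cost improvement in safety ascertainment. It does not touch the efficacy analysis.

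**What to change.** 1. In section 8.1, limit the third bullet of the hospitalization exceptions to admissions planned before randomisation, so that it agrees with the AE, SAE and preexisting-condition definitions and with section 8.2.
2. Capture every unplanned alcohol-related admission, including intoxication, withdrawal, detoxification and relapse, as an AE or SAE. Record causality after capture, with baclofen, alcohol or both as the options.
3. Show these admissions as a separate line by arm in the DSMB summaries and the final safety tables.

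The cost is an edit to the reporting text and a few more forms, with no added visit or procedure. The downside is an SAE count that includes some events due to alcohol alone; the separate line keeps them distinguishable.

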### **8.2 Recording of Adverse Events**

At each contact with the subject, the investigator must seek information on adverse events by specific questioning and, as appropriate, by examination. Information on all adverse events should be recorded immediately in the source document, and also in the appropriate adverse event module of the case report form (CRF). All clearly related signs, symptoms, and abnormal diagnostic procedures results should be recorded in the source document, though should be grouped under one diagnosis.

All adverse events occurring during the study period must be recorded. The clinical course of each event should be followed until resolution, stabilization, or until it has been determined that the study treatment or participation is not the cause. Serious adverse events that are still ongoing at the end of the study period must be followed up to determine the final outcome. Any serious adverse event that occurs after the study period and is considered to be possibly related to the study treatment or study participation should be recorded and reported immediately.

### **8.3 Reporting of Serious Adverse Events and Unanticipated Problems**

Investigators and the protocol sponsor must conform to the adverse event reporting timelines, formats and requirements of the various entities to which they are responsible, but at a minimum those events that must be reported are those that are:

- related to study participation,
- unexpected, and
- serious or involve risks to subjects or others  
(see definitions, section 8.1).

If the report is supplied as a narrative, the minimum necessary information to be provided at the time of the initial report includes:

- |   |   |
|---|---|
| 
 
• Study identifier
 
• Study Center
 
• Subject number
 
• A description of the event
 
• Date of onset
 
 | 
 
• Current status
 
• Whether study treatment was discontinued
 
• The reason why the event is classified as serious
 
• Investigator assessment of the association between the event and study treatment
 
 |
|---|---|

### 8.3.1 Investigator reporting:

For reportable deaths, the initial submission to the UNC IRB may be made by contacting the IRB Director or Associate Director. The AE/Unanticipated Problem Form is required as a follow up to the initial submission.

#### Other Reportable events:

For clinical drug trials, the following events are also reportable to the UNC IRB:

- Any adverse experience that, even without detailed analysis, represents a serious unexpected adverse event that is rare in the absence of drug exposure (such as agranulocytosis, hepatic necrosis, Stevens-Johnson syndrome).
- Any adverse event that would cause the sponsor to modify the investigators brochure, protocol or informed consent form, or would prompt other action by the IRB to assure protection of human subjects.
- Information that indicates a change to the risks or potential benefits of the research, in terms of severity or frequency. For example:
  - An interim analysis indicates that participants have a lower rate of response to treatment than initially expected.
  - Safety monitoring indicates that a particular side effect is more severe, or more frequent than initially expected.
  - A paper is published from another study that shows that an arm of your research study is of no therapeutic value.
- Change in FDA safety labeling or withdrawal from marketing of a drug, device, or biologic used in a research protocol.
- Breach of confidentiality
- Change to the protocol taken without prior IRB review to eliminate apparent immediate hazard to a research participant.
- Incarceration of a participant when the research was not previously approved under Subpart C and the investigator believes it is in the best interest of the subject to remain on the study.
- Complaint of a participant when the complaint indicates unexpected risks or the complaint cannot be resolved by the research team.
- Protocol violation (meaning an accidental or unintentional deviation from the IRB approved protocol) that in the opinion of the investigator placed one or more participants at increased risk, or affects the rights or welfare of subjects.

### 8.3.2 Sponsor reporting: Notifying the FDA

The study sponsor is required to report certain study events in an expedited fashion to the FDA. These written notifications of adverse events are referred to as IND safety reports. The following describes the safety reporting requirements by timeline for reporting and associated type of event:

- ***Within 7 calendar days***

Any study event that is:

- associated with the use of the study drug
- unexpected,
- fatal or life-threatening, and

- ***Within 15 calendar days***

Any study event that is:

- associated with the use of the study drug,
- unexpected, and
- serious, but not fatal or life-threatening
  - or-
- a previous adverse event that was not initially deemed reportable but is later found to fit the criteria for reporting (reporting within 15 calendar days from when event was deemed reportable).

Any finding from tests in laboratory animals that:

- suggest a significant risk for human subjects including reports of mutagenicity, teratogenicity, or carcinogenicity.

**Additional reporting requirements**

Sponsors are also required to identify in IND safety reports all previous reports concerning similar adverse events and to analyze the significance of the current event in light of the previous reports.

**Reporting Process**

Adverse events will be submitted on FDA Form 3500A or in a narrative format, along with FDA form 1571. If supplied as in a narrative format, the minimum information to be supplied is noted above at the beginning of section 8.3.

**8.4 Unblinding Procedures**

The randomization schedule will be given to IDS personnel; investigators will not have access to this information. If a medical or other emergency necessitates breaking the blind, IDS personnel will provide the identity of the medication to the PI or another medical study team member. This will be recorded in the subject's study record.

**8.5 Stopping Rules**

The Data Safety Monitoring Board (DSMB) will provide a summary letter to the PI and to the IRB regarding any safety concerns and a recommendation as to whether the study should be stopped or modified for safety reasons. No a priori stopping rules will be established for this Phase II trial.

A subject who experiences a serious adverse event thought to be possibly or probably related to study medication will have their medication tapered and stopped. It is preferable to taper baclofen then stopping it abruptly. If a subject is having moderate side-effects the medication can be reduced and side-effects monitored. If a subject continues to have side-effects the medication may be tapered and stopped. We will make every effort to maintain subjects in the trial as long as safety is adhered to. If a subject does not comply with medication instructions we may need to discontinue medication for safety purposes. We will follow subjects off medication to collect outcome data such as drinking behavior.

